### 6.3 *Describe:*

- *Procedures performed to lessen the probability or magnitude of risks.*
- *All drugs and devices used in the research and the purpose of their use, and their regulatory approval status.*
- *The source records that will be used to collect data about subjects. (Attach all surveys, scripts, and data collection forms.)*

To lessen the probability or magnitude of risks, researchers will stop testing or administer breaks if participants feel frustrated, tired, and/or uncomfortable. Additionally, the occurrence of any adverse events associated with this study and its procedures, as well as any changes in risk level, will be monitored by the principal investigator and co-investigators

For fMRI, additional risks and preventions include: 1) Magnetic field attracting ferromagnetic objects: Subjects will be screened for metallic objects prior to entering the scan room to minimize this risk and anyone with a questionable history of metal will not be allowed to enter the scanner room. 2) Claustrophobia: Any participant reporting the experience of claustrophobia will be removed from the magnet immediately, debriefed, and given compensation for their time. 3) Noise: All participants will be required to wear ear plugs to shield them from scanner noise while allowing communication from the technician. If the noise is overly bothersome to the subjects, they will be removed from the magnet immediately. Please note: The occurrence of any adverse events associated with this study and its procedures, as well as any changes in risk level will be monitored by the principal investigator and coinvestigators of this study, as well as the scanner technician.

For TMS, the most severe risk is that of seizure. The risk of seizure will be minimized in two ways 1) Using stimulation parameters that are within the safety guidelines reported by Rossi et al., 2009 and updated by Rossi et al., 2021, and 2) Screening and excluding participants with increased seizure risk as indicated by Rossi et al., 2009 and Rossi et al., 2021. As extensively detailed in section 15.1 below, risk for seizure is very low, even for individuals with elevated risk. Due to our interest in individuals with elevated anhedonia, we will not be able to exclude individuals with psychiatric disorders (i.e. major depression) and/or individuals receiving medications to treat psychiatric disorders, both of which increase seizure risks. However, we will screen for other factors that increase seizure

PROTOCOL TITLE:

risks and exclude participants accordingly. See section 15.1 for further details of seizure risks.

Personnel who administer TMS will be trained to recognize a potential seizure event and to act as first responders in order to administer appropriate initial care. In addition, all study personnel will be trained in Basic Life Support and CPR usage. However, we wish to emphasize that there are no known cases where individuals required the use of CPR during a TMS session. The major physical signs the study personnel will look out for in detecting a potential seizure include chewing movements, convulsions/tremor/shaking, difficulty talking, a blank stare, eyes rolling up, and profuse sweating. If any of these signs are observed, study personnel will stop the research procedure and inquire whether the subject feels okay. If the subject is unresponsive (and therefore likely experiencing a seizure), first-aid will be supplied. The first-aid response consists of making sure the subject is physically safe for the duration of the seizure. This involves moving the subjects out of the TMS chair and onto the floor lying down on their left side. The subject will be kept lying down on their left side, while the staff call emergency medical help, via a 911 call. Resources available in the laboratory include a first-aid kit and immediate phone access. In the extremely unlikely event of an actual occurrence of a seizure, it will be immediately reported to the IRB. To minimize headaches and/or other forms of discomfort, the experimenter will encourage participants to report any form of discomfort during the procedure. The experimenter will periodically directly query the participant regarding whether or not they are experiencing discomfort. In addition, an arm will be used to help support the coil to reduce downward pressure on the subject that could lead to neck discomfort. The experimental procedure will be immediately terminated whenever anyone reports experiencing discomfort. To prevent adverse effects on hearing due to the sound produced by TMS, all experimental participants will wear ear plugs.

In order to ensure that personnel are qualified to administer TMS, all personnel to be added to this protocol will receive a minimum of 10 hours of training with an experienced TMS administrator. In addition to training, personnel will be required to read safety documentation consisting of Rossi et al., 2009, and Oberman et al., 2011. Prior to being permitted to administer TMS, all personnel will meet with [name] to ensure understanding of the TMS procedure and all potential

contraindications. All personnel will receive CPR training and CITI training. Additionally, all personnel will be instructed on how to deal with a seizure.

The source records that will be used to collect data about subjects will be retained in digital format. Digital information will be stored on password protected local machines, or on secure cloud-based services such as Google Docs, also requiring a password.

Due to the COVID-19 national emergency and pandemic, researchers will also apply the following precautions in conducting this research:

- No persons deemed as higher risk by the CDC will be included in the study. Participants will be screened such that they meet these requirements.
- COVID-19 related risks will be mitigated as much as possible. This will be done through screening for exposure to COVID-19, regular cleaning and disinfecting study areas, reducing in-person interactions, and use of personal protection equipment.
- To prevent the spread of pathogens during TMS, participants may be given a disposable face mask. Administered masks will contain no metal so as to be compatible with TMS.

For in-person study activities involving prospective subjects and study staff, we will as part of our screening and eligibility procedures implement the option of informing subjects and staff that their voluntary disclosure of their full COVID-19 vaccination status is an alternative to the requirement for COVID-19 precautions such as social distancing, use of masks, and other safety precautions. In doing so, we will use the following language: "In order to protect against COVID-19 or Coronavirus, if you come to the lab we are required to follow certain precautions like social distancing and use of masks. However, we don't have to do this for persons who have completed a full COVID-19 vaccination. You may if you'd like share with us information about your COVID-19 vaccination, but this is your decision and is not required. You can still come to the lab and we will follow our usual COVID-19 precautions."

To implement this COVID-19 vaccination option, we will make a note in our study records for each prospective subjects and

PROTOCOL TITLE:

staff who choose to disclose their COVID-19 vaccination information

**6.4** *What data will be collected during the study and how that data will be obtained.*

The data that will be collected during the study includes identifying information. Additionally, brain activations, accuracies and reaction times to tasks will be collected. The data will be obtained using computerized-based tasks or written tasks while being tested in the MRI scanner.

**6.5** *If there are plans for long-term follow-up (once all research related procedures are complete), what data will be collected during this period.*

In some cases, performance in some tasks will trigger eligibility for other tasks. In these cases, procedures will be identical to those described above.

**6.6** *For Humanitarian Use Device (HUD) uses provide a description of the device, a summary of how you propose to use the device, including a description of any screening procedures, the HUD procedure, and any patient follow-up visits, tests or procedures.*

NA

**7.0 Data and Specimen Banking\***

**7.1** *If data or specimens will be banked for future use, describe where the specimens will be stored, how long they will be stored, how the specimens will be accessed, and who will have access to the specimens.*

NA

**7.2** *List the data to be stored or associated with each specimen.*

NA

**7.3** *Describe the procedures to release data or specimens, including: the process to request a release, approvals required for release, who can obtain data or specimens, and the data to be provided with specimens.*

NA

**8.0 Sharing of Results with Subjects\***

**8.1** *Describe whether results (study results or individual subject results, such as results of investigational diagnostic tests, genetic tests, or incidental findings) will be shared with subjects or others (e.g., the subject's primary care physicians) and if so, describe how the results will be shared.*

The MRIF contracts with The Mind Research Network (MRN) for screening of all subjects. To this end, subjects electing to partake in the IF program will have their T1 and T2 weighted scan data sent to MRN via encrypted data link. Other scans such as Susceptibility Weighted Images (SWI), Diffusion Weighted Images (DWI), and Fluid-attenuated Inversion Recovery (FLAIR) can also be sent to MRN for review, if needed.

The MRN Contracted Radiologists will review images provided to them, and do not have access to additional clinical information. The MRI scans are collected under research protocols and are not obtained for clinical purposes.

The research MRI scans are not a substitute for a clinical scan and might not show problems that may be picked up by a clinical scan. If MRNs find an abnormality that requires follow-up, they may also mail a copy of the report to the subject, or contact them (with their permission), to help answer questions.

All MRN radiology reviews are completed within 30 days and are forwarded as a de-identified report directly to the MRI Technologist. All reports are then printed and mailed via US Postal Service to the subject's mailing address. They are provided with the contact information of the MRI Technologist in case they have questions. Any returned reports will be recorded and the hard copy destroyed.

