## 13.0 Recruitment Methods

*13.1 Describe when, where, and how potential subjects will be recruited.*

Recruitment will be conducted at Florida State University at least one hour before testing. Potential subjects will be recruited via voluntary responses to flyers posted around campus, at the FSU Behavioral Health Clinic at Apalachee Center Clinic, FSU Psychology Clinic, community spots (i.e. coffee shops and restaurants) and responses to approved electronic postings (see Appendix). In addition, subjects may be reached out to via an 'Okay to be Contacted' list that was collected/provided by [name], a member of the FSU College of Medicine (FSU STUDY #STUDY00002548: FSUN Future Contact Registry), via the SONA system at FSU where potential subjects will read about and sign up for the study on the SONA system or via ResearchMatch which is a national electronic, web-based recruitment tool that was created through the Clinical & Translational Science Awards Consortium in 2009 and is maintained at Vanderbilt University (they maintain the IRB approval for the Research Match database creation and recruitment). Additionally, flyers will be given to participants who have volunteered for similar studies. (A paper flyer will be given to participants who have volunteered for similar studies after they have completed the study. These participants will have completed a study in a lab at Florida State University that uses similar methods to us and has agreed to hand out flyers for our studies to their participants). Volunteers will email or call a trained research technician who will screen the subject by the stated criteria. DARS will be completed electronically to identify eligible participants. Potential subjects that pass initial screening will be instructed to meet either in the [name] lab in the Psychology Building, [name] lab in the Psychology Building, or the MRI facility at the College of Medicine. All of these are private and secure locations requiring key card access.

*13.2 Describe the source of subjects.*

The source of subjects will be from Florida State University or the local community as long as subjects are eligible based on inclusion and exclusion criteria.

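### Section 8.1 gives no step for reaching a participant whose mailed MRI report is returned, even when the report states an abnormality needing follow-up

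*Combined protocol and SAP*

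**What the plan says.** The procedure is in section 8.1 (Sharing of Results with Subjects) of the combined protocol and SAP.

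- **Who is covered.** Only those who opt in: "subjects electing to partake in the IF program will have their T1 and T2 weighted scan data sent to MRN via encrypted data link".
- **Review.** "All MRN radiology reviews are completed within 30 days and are forwarded as a de-identified report directly to the MRI Technologist".
- **Delivery.** "All reports are then printed and mailed via US Postal Service to the subject's mailing address".
- **Questions from the participant.** "They are provided with the contact information of the MRI Technologist in case they have questions".
- **Failed delivery.** "Any returned reports will be recorded and the hard copy destroyed".
- **Abnormality needing follow-up.** For this case the section adds that MRN has an option: "they may also mail a copy of the report to the subject, or contact them (with their permission), to help answer questions".

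The study has other ways to reach participants. Section 10.1 describes screening by e-mail, by phone and in person, and section 13.1 says: "Volunteers will email or call a trained research technician who will screen the subject by the stated criteria".

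**The concern.** An incidental-findings programme is useful only if a participant with a finding hears of it. Section 8.1 foresees that letters will sometimes come back, and the step it then sets concerns the paper: log the return and dispose of the copy. From that moment the study knows that the participant has not received the report by the required route, but nobody is assigned to try another.

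The gap matters most for a report stating an abnormality that needs follow-up, because that participant loses the chance to act on it. The section does not separate such a report from a normal one at this step. The issue is participant safety and record handling; no endpoint or analysis depends on it.

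**Working it through.** No arithmetic applies. The plan states no figure for this process, and none can be derived from what it gives. The check is to follow a report through section 8.1 and then look elsewhere in the document for a fallback.

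1. **Required path.** A participant opts in; MRN reviews the scan within 30 days; the de-identified report goes to the MRI Technologist; it is printed and posted. This is a single channel, and it is the same for normal and abnormal reports.

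2. **The letter is returned.** The stated actions are to record the return and destroy the hard copy. Section 8.1 mentions no address check, second mailing, phone call, e-mail or notice to the investigator.

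3. **Could the MRN option fill the gap?** It applies only to abnormalities needing follow-up.
   - It is worded as something MRN may do, not something it will do.
   - It has two arms. One is another letter, which fails again if it goes to the same wrong address. The other is direct contact, which could succeed but depends on the participant's permission.
   - Its stated purpose is to help with questions. Nothing says that MRN is told of a returned letter, so failed delivery does not set it in motion.

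4. **Could the participant fill the gap?** Participants are given the MRI Technologist's contact details for questions. Someone who has received no report may not know that there is anything to ask.

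5. **Is there a fallback elsewhere?** No other section of the document sets out a route for returning incidental findings.

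6. **Are other means of contact available?** Phone and e-mail are in use from screening onward (sections 10.1 and 13.1). A later visit is less dependable. Section 9.1 promises at least one session and only possibly more. The Study Summary gives 4 to 5 weeks of participation, which is 4 × 7 = 28 to 5 × 7 = 35 days. A review that takes the full 30 days could therefore arrive near or after the last visit.

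The result is one required channel, one discretionary channel that is not linked to failed delivery, and no required step after a letter comes back.

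**The case against.** The strongest reply is that the sentence on returned reports governs disposal of a paper health record and says nothing about contact. Several stronger readings are tempting, and the documents do not support them.

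- **That the plan rules out further contact.** This would be inferred from silence. Section 8.1 specifies no further attempt, but it does not forbid one.
- **That the result itself is lost.** Only the hard copy is destroyed. The report went to the MRI Technologist before it was printed, and nothing says that this source report or the log entry is discarded.
- **That there is no other route for an abnormal finding.** The MRN option exists, and its direct-contact arm could reach some participants.
- **That every participant is exposed.** Only those who join the IF programme are.
- **That a given share of participants would be missed.** Any percentage would need assumed rates of returned mail, abnormality and opt-in. The Study Summary gives a sample size of 80 and section 12.1 gives 150 accrued locally, but neither is a count of participants scanned and opted in.
- **That the 30 days make addresses out of date.** That figure is the time limit for the review and says nothing about addresses.

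It is also fair to say that the consent document, which section 23.3 says is attached, is not in the text reviewed and may cover contact permission or a fallback. In addition, the MRI facility holds the contract with MRN, so part of the practice may lie outside this protocol.

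These points narrow the concern without removing it. The plan states a rule for failed delivery, and someone can follow that rule completely while a participant with an abnormality needing follow-up remains uninformed.

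**Conclusion.** The concern holds in a limited form. For participants in the IF programme, section 8.1 requires one posted letter. If that letter is returned, the section requires only that the return be logged and the paper destroyed, whatever the report says. An abnormal finding could then go uncommunicated after delivery is known to have failed, unless MRN chooses to act and, for direct contact, has permission, or staff do more than the text asks.

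The number of participants affected cannot be estimated from the documents. The case for change rests on the possible seriousness of a single missed finding and the low cost of preventing it. The conclusion assumes that no fallback is set out in the consent document or the MRI facility's own procedure. If one is, section 8.1 should refer to it and agree with it.

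**What to change.** Amend the sentence on returned reports in section 8.1 so that it states the following:

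- A returned report is recorded. Before the hard copy is destroyed, the MRI Technologist or study staff try to reach the participant by the phone or e-mail already held, within the contact permission given at consent.
- Reports stating an abnormality that needs follow-up are handled first.
- Each attempt is documented. The sponsor sets how many attempts are made before the copy is destroyed.

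The step should keep to the existing path of the de-identified report through the MRI Technologist and should not rely on a remaining visit. The wording needs to agree with the consent form and with the MRI facility's procedure, so editing one sentence may not be enough.

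The cost is a few calls or e-mails and slightly longer secure storage of the paper copy. This is a notification and record-keeping step; no clinical action on any finding is proposed.

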## 9.0 Study Timelines\*

### 9.1 Describe:

- *The duration of an individual subject's participation in the study.*
- *The duration anticipated to enroll all study subjects.*
- *The estimated date for the investigators to complete this study (complete primary analyses)*

The duration for each individual's participation will be between 30 minutes and 2 hours per session. Participants will participate in at least 1, and potentially several sessions. It may take up to several weeks to complete an entire task. The duration anticipated to enroll all study subjects is 72 months.

## 10.0 Inclusion and Exclusion Criteria\*

### 10.1 Describe how individuals will be screened for eligibility.

Participants will be screened in order to minimize risks associated with TMS and fMRI. Screening will proceed with a combination of e-mail, phone, and in person questions. First, the screening forms will be sent to the participant via e-mail (see Appendix), performed

over the phone, or both. If the participant passes the first phase of screening and remains interested in participating, the participant will be invited to perform the study. Participants will read the consent form and any questions will be answered. Screening for TMS will be completed again in each experimental session to assess if any changes have occurred prior the last screening. The individuals included in this study will be adults from ages 18 to 55.

We will also exclude from study individuals who are vulnerable to or may have come in contact with COVID-19. We will include individuals who have completed a full FDA-authorized vaccination series at least 14 days before the study session, and individuals who have not been fully vaccinated provided that they pass the screening process. As with the other screening forms, the COVID-19 screening form will be sent to the participant via e-mail (see Appendix). The participant will be asked to respond with whether the answer to question #1 on the form is “yes” or if, alternatively the answer to #1 is “no” and the answer to any other question on the screening form (#2 through #8) is “yes.” Question #1 asks participants to indicate if they have received a complete vaccination series, the specific FDA-approved vaccine product they received, and the date of vaccination. At this phase, the participant does not need to indicate which to which of the other questions the answer is “yes.” If the response is “yes” to any questions including #2 through #8, the participant will be excluded. If the participant passes the first phase of screening and remains interested in participating, the participant will be invited to perform the study. Participants will read the consent form and any questions will be answered. After answering questions, the participant will once again be presented with the screening form. In this case, the participant will fill-out the screening form. If the answer is “no” to #1 and “yes” to any of the other questions (#2 through #8), the participant may be asked to elaborate. A “yes” response may occur in the second screening, but not the first, if circumstances changed since the initial screening.

Finally, screening for this study will also involve completing the Dimensional Anhedonia Rating Scale (DARS); only participants who score 46 or below (i.e., those who endorse increased anhedonia) are eligible.

10.2 *Describe the criteria that define who will be included or excluded in your final study sample.*

Inclusion: Because we are interested in the mental function of adults prior to any age-related decline, participants will be between the ages of 18-55. Participants will also need to be fluent in English and have

PROTOCOL TITLE:

acquired fluency prior to the age of 6 since English is required to understand the instructions. Because of the visual presentation of stimuli, participants will need to have normal or corrected-to-normal vision. Only participants who score 46 or below on the Dimensional Anhedonia Rating Scale (DARS) are eligible.

**Exclusion:** Left-handed people will be excluded. Many brain functions are lateralized (e.g. language is often processed by the left hemisphere). While such lateralization is typically very consistent in right-handers, brain lateralization is less predictable in left-handers which can confound localization of function. Participants must pass the MRI screening protocol, excluding people who have metal in any portion of the body, have medical complications, cardiac pacemaker cochlear implant, aneurysm clip, IUD shrapnel, history of metal fragments in eyes, neurostimulators, weight over 300 pounds, known problems of claustrophobia, or illicit drug use. Because alcohol has a transient effect on neural activity, subjects will be screened to have not consumed alcohol for the past 24 hours via self-report.

Additionally, people with the following will be excluded: hearing impairments and permanent retainers on the top portion of their jaw. A screening form (attached) will be used to assess each subject's eligibility for participation.

